### Primary Outcomes

- Ability to identify danger signs in pregnancy (e.g. bleeding, severe headache, blurred vision, fever)
- Birth preparedness and complication readiness (e.g. saved money, identified birth facility and emergency transportation to facility, blood donor)
- Ability to identify newborn danger signs (e.g. poor suck, jaundice, difficulty/fast breathing, and convulsions)

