### Secondary Outcomes

- Uptake of modern family planning methods at 6 months postpartum
- Infant immunized per EPI scheduled at 1 year
- Completion of IPTp2 malaria prophylaxis during pregnancy

**Aim 3:** To evaluate the clinical outcomes of mothers and their newborns (e.g. decrease in maternal morbidities and perinatal and neonatal mortality)

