### 3.3 Data Collection and Measures

All quantitative data will be collected by trained RAs using encrypted and password protected tablets and the REDCap secure web application for data collection database management. Redcap, a secure web application, is geared to support online or offline data capture for research studies. When internet connection is not available, data will be collected off-line and stored on the encrypted tablet. Once a connection is available, these data will be uploaded, managed, and stored on a secure server.

No data will be collected by clinical providers. Data collection will occur at five time points in both intervention and control arms:

1. Time 0: at ENROLLMENT (in person)
  2. Time 1: at THIRD TRIMESTER (in person)
  3. Time 2: POST BIRTH up to 6 weeks after delivery (in person)
  4. Time 3: SIX MONTHS POSTPARTUM (by phone)
  5. Time 4: ONE YEAR POSTPARTUM (by phone)
- 
- 1) T0: The baseline session occurs immediately following the consent process and will be held for approximately 1 hour. Data will be collected by trained RAs using a structured survey; medial information will be self-reported, and thus, are not protected health information (PHI).
  - 2) T1: This session will occur at the third trimester of pregnancy and will last 45 – 60 minutes. Data will be collected by trained RAs using a structured interview and retrieving data from the ANC card. Data collected from the ANC card are PHI and will be protected.
  - 3) T2: This session will occur in the period immediately to 6 week after delivery and will last 45 – 60 minutes. Data will be collected by trained RAs using a structured interview and information from ANC cards on maternal and newborn clinical outcomes using a pre-determined set of indicators.
  - 4) T3: This session will occur 6-months postpartum; data will be collected via phone by a trained RAs using a structured interview. This session will take approximately 20 - 30 minutes.
  - 5) T4: This session will occur 1-year postpartum; data will be collected via phone by a trained RAs using a structured interview. This session will take approximately 20 - 30minutes.

During all visits midwives will record Clinical Health Related Outcomes (Place of birth, hemoglobin levels, newborn birth weight, maternal & newborn morbidities, stillbirth, postpartum visit within 2 days post birth) on the women's ANC card. These data will be collected by the RA during all study visits except baseline.

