## Measures

Time Point	Domain	Data collection
T0 – Baseline	Demographic Characteristics (Age, gravida, living children, marital status, age at marriage, pregnancy history, medical history)	Face-to-face Survey
	Self-efficacy	
	Recognize problems and understands health information	Face-to-face Survey
	Care-seeking history	Face-to-face Survey
	Educational Background	
	Level of Education	Face-to-face Survey
	Prior Knowledge	
	Ability to identify danger signs/BPCR	Face-to-face Survey
	Health Literacy Skills (understanding, engagement with health system)	Face-to-face Survey
	Ecological Influences (social support, community and family resources)	Face-to-face Survey
T1 – Third trimester	Comprehension of Stimuli (identification of danger signs, BPCR)	Face-to-face Survey
	Self-determination	
	Intent to use family planning / preparation for birth	Face-to-face Survey
	Two or more tetanus toxoid vaccines / Completion of ITP 2 malaria prophylaxis	ANC Card
T2 – Post birth	Clinical Health Related Outcomes (Place of birth, hemoglobin levels, newborn birth weight, maternal & newborn morbidities, stillbirth, postpartum visit within 2 days post birth)	ANC Card
	Self-determination	
	Attendance at 4 or more ANC visits	ANC Card
	Adherence to care - Number of ANC Visits	ANC Card
	Health Related Behavior (Maternal and newborn postpartum visits)	Survey
	Clinical Health Related Outcomes (Perinatal mortality (<7 days), maternal morbidities)	ANC Card
T3 – Six months postpartum	Health Related Behavior (Uptake of modern family planning, exclusive breastfeeding, 4 postnatal check-ups completed on both mother and newborn in first 6 weeks)	Survey via phone
	Clinical Health Related Outcomes (Neonatal mortality(<28 days), maternal morbidities)	Survey via phone
T4 – One year postpartum	Health Related Behavior (Repeat pregnancy)	Survey via phone
	Clinical Health Related Outcomes (Infant immunized per EPI schedule; maternal morbidities)	Self-report Survey via phone

During all visits midwives will record Clinical Health Related Outcomes (Place of birth, hemoglobin levels, newborn birth weight, maternal & newborn morbidities, stillbirth, postpartum visit within 2 days post birth) on the women's ANC card. These data will be collected by the RA during all study visits except baseline.

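### Infant immunisation to schedule at one year rests only on unverified phone self-report, and the plan does not say whether a record is consulted

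*Combined protocol and SAP*

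**What the plan says.** Section 2.0 names "Infant immunized per EPI scheduled at 1 year" as a secondary outcome of Aim 2. The Measures table in section 3.3 places it at T4 as "Infant immunized per EPI schedule; maternal morbidities", with the source "Self-report Survey via phone". The T4 description agrees: "This session will occur 1-year postpartum; data will be collected via phone by a trained RAs using a structured interview". The call is planned to last 20 to 30 minutes.

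The same table takes "Two or more tetanus toxoid vaccines / Completion of ITP 2 malaria prophylaxis" from the ANC card. Section 3.3 also lists clinical items that midwives enter on the ANC card and adds "These data will be collected by the RA during all study visits except baseline". Infant immunisation is not on that list. No child health record, facility register or validation subsample is named for it anywhere. The plan does not list the vaccines, doses or age windows that make an infant complete.

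Under section 4.0, a binary secondary outcome of Aim 2 is analysed with a logit mixed model with a random intercept for the 14 facilities. The effect measure is an odds ratio, tested at 0.05.

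**The concern.** Whether an infant is immunised to schedule is a statement about which doses were given and at what age. The plan uses a written record for a simpler fact about the mother and self-report for this more complex fact about the child. Without a definition and a recorded source, two analysts could classify the same infant differently, and nobody could later tell documented answers from remembered ones.

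The likely error is over-reporting. Its effect depends on whether it is equal between arms. Equal error weakens a real effect. The plan describes no blinding of women or research assistants, and group care delivers repeated health messages, so error could also be greater in the intervention arm. That would push the result towards group care. As planned, the data could not separate these two situations.

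**Working it through.** **Inputs.** The plan gives no immunisation rate, reporting accuracy, intracluster correlation (ICC) or power for this outcome, so it has no figure of its own to reproduce. All rates, sensitivities (Se), specificities (Sp) and ICCs below are assumptions. From the documents: 1680 women (section 3.0) and 14 facilities, 7 per arm (section 3.7), hence 1680/14 = 120 per facility and 840 per arm.

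**Formula.** Observed proportion = p × Se + (1 − p) × (1 − Sp). With equal error in both arms, observed risk difference = true risk difference × (Se + Sp − 1).

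**1. Equal over-reporting, true 75% vs 82%, Se 0.97.** True OR = (0.82/0.18)/(0.75/0.25) = 1.52.

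| Sp | Control observed | Intervention observed | Difference | OR |
|---|---|---|---|---|
| 0.8 | 0.7275 + 0.25×0.2 = 0.7775 | 0.7954 + 0.18×0.2 = 0.8314 | 7 × 0.77 = 5.4 points | 1.41 |
| 0.4 | 0.7275 + 0.25×0.6 = 0.8775 | 0.7954 + 0.18×0.6 = 0.9034 | 7 × 0.37 = 2.6 points | 1.31 |

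The risk difference keeps 77% and 37% of its true size. The planned measure is hit less hard: the log odds ratio keeps ln 1.411/ln 1.519 = 82% and ln 1.306/ln 1.519 = 64%.

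**2. Power under equal over-reporting.** Separate assumptions: true 70% vs 80%, Se 1, ICC 0.01, no dropout, two-sided 0.05 without the Holm adjustment. Design effect = 1 + 119 × 0.01 = 2.19, so the effective size is 840/2.19 = 384 per arm. The calculation is a normal approximation without a correction for few clusters.

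- Sp 1: difference 0.10, OR 1.71, power 0.89.
- Sp 0.7: 0.79 vs 0.86, difference 0.07, OR 1.63, power 0.72.
- Sp 0.5: 0.85 vs 0.90, difference 0.05, OR 1.59, power 0.55.

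At ICC 0.05 the corresponding powers are 0.43, 0.30 and 0.22. When sensitivity is perfect the odds ratio moves little; the loss is mainly in the risk difference and in power.

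**3. Unequal over-reporting, no true effect.** With 75% in both arms, Se 0.97, and Sp 0.6 in control and 0.5 in intervention: control = 0.7275 + 0.25×0.4 = 0.8275; intervention = 0.7275 + 0.25×0.5 = 0.8525. The spurious difference is 2.5 points, and OR = (0.8525/0.1475)/(0.8275/0.1725) = 1.20.

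With 70% in both arms, Se 1 and Sp 0.7 vs 0.5, the observed rates are 0.79 vs 0.85 (OR 1.51). The chance of a significant result favouring group care is about 58% at ICC 0.01 and 23% at ICC 0.05.

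**4. Unequal over-reporting with a true effect.** True 70% vs 80%, Se 1, Sp 0.7 vs 0.5: observed 0.79 vs 0.90, difference 0.11, OR 2.39 against a true 1.71. The effect is enlarged.

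**The case against.** The plan does not say that the answer is unaided or from memory. A reader might infer both from the label, but a structured interview leaves room for a mother to look at a record. A reader might also infer a single yes/no question; the T4 questionnaire is not in the documents and could ask dose by dose. Both objections stand. What the documents support is that the stated source is self-report, that no verification is named, and that the use of a record is left open.

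A reader might infer that group care teaches immunisation, so that its women have learned the approved answer. The documents do not show this. Section 2.0 has "Ability to identify newborn danger signs (e.g. poor suck, jaundice, difficulty/fast breathing, and convulsions" as a primary outcome, which is newborn content, but neither that nor section 3.5 mentions immunisation. Greater over-reporting in the intervention arm is therefore plausible and no more.

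It is also tempting to say that over-reporting shrinks any true difference. That holds only when error is equal between arms; item 4 of the working shows the reverse. Attenuation and spurious benefit are alternative scenarios.

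Finally, section 3.1 expects many women to be unable to read, so simply asking mothers to read out dates would fail for some. This stands and shapes the fix.

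**Conclusion.** The concern holds as a modest measurement weakness in one secondary outcome. For infant immunisation the plan names a weaker source than it uses for the mother's vaccines, and it leaves both the definition of completion and the use of a record open. Under the assumed inputs, equal over-reporting takes a true odds ratio of 1.52 down to between 1.41 and 1.31. A gap of 0.1 in specificity between arms produces an odds ratio of about 1.2 where there is no effect. None of these inputs comes from the documents, so the figures show what kinds of error are possible and do not estimate the error in this trial. No primary outcome and no sample-size figure depends on this item.

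**What to change.** - **Before the call:** when scheduling T4, ask the mother to have the infant's immunisation record at hand.
- **During the call:** have her, or a household member who can read, read out each dose and date. If that is not possible, ask about each dose in turn from recall.
- **Definition:** pre-list the doses and age windows that the trial's EPI schedule implies, and derive completion from the entries in REDCap.
- **Source:** record for each infant whether the entries came from a record or from recall, and report this by arm.
- **Analysis:** keep all infants in the main model. Present a record-only result as exploratory. Having and reading a record arises after randomisation, and because improved health literacy is the trial's hypothesis it may differ by arm. That subset is therefore not an unbiased check on the full result.

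**Cost:** a few more minutes on a call already planned and a revised T4 form, with no extra visit or staff. Infants whose mothers have no record, or nobody able to read it, remain recall-only. The error is reduced and made visible, but not removed.

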### **3.4 Process Evaluation**

We will concurrently conduct a process evaluation to identify and document patient, provider, and system barriers and facilitators to program implementation. Using both quantitative and qualitative methods, we will identify potential and actual influences on the quality and conduct of the program's operations, implementation, and service delivery.

**Data Collection (Process Evaluation):** Process evaluation data will be collected via audiotaped semi-structured interviews with facility staff and women participating in GANC. Process evaluation data will include an assessment of both providers' and women's perceptions.

All midwives (providers) involved in the intervention arm (GANC) will be asked to participate in the process evaluation. Midwives will be approached by the RA at the end of the 7th group meeting and asked if they are interested in providing feedback about group care. Those willing to participate will be taken through a consent process before the first interview begins. Each midwife will be interviewed at two random times and each interview will last approximately 40 minutes. A structured interview using open-ended questions will be conducted to explore the midwife's perceptions of group versus standard ANC, barriers to implementation, challenges to integrating it into the existing clinic workflow, and strategies that have helped with implementation. Interviews will be audiotaped (with permission from the participant) to ensure accuracy of responses; midwives can refuse to be audiotaped yet continue with the interview. The RA will write short answer responses on a data collection form. Audio tapes will be transcribed and will be de-identified; tapes will be destroyed immediately after transcription. We have 7 health facilities randomized to the intervention arm and 2 to 4 midwives at each facility; As each midwife may be interviewed twice, we expect approximately 56 midwives may participate in the process evaluation.

Groups of women in the intervention arm will be randomly selected to participate in focus groups for process evaluation. We anticipate 10 random groups of 10 women through the course of the study for a total of 100 women in focus groups. Women will be asked to describe their perceptions of group versus standard ANC, their perceptions of the value of group ANC, and how they could envision the process being improved. Each focus group discussion will last about 1 hour. Women will be given a small baby gift for their participation.

We will employ structured observations of group sessions, interviews with providers, focus groups

of women, and tracking logs to record how the intervention is delivered and received, document program fidelity, and identify opportunities to enhance the delivery of the intervention, while maximizing consistency in intervention delivery across sites. This process evaluation will add value to the analysis of the group ANC intervention by identifying barriers and facilitators at multiple levels throughout the study. For this process evaluation we will focus on both fidelity of the intervention and dose (or frequency).

We will not conduct focus groups with women in the control arm or interviews with midwives at facilities in the control arm as the intent of the focus group is to glean information about women's experience in GANC.

**Structured Observations:** A sample of 2 of 7 group ANC visits will be observed for each provider to monitor fidelity to the model (e.g. if content is delivered as intended, women are engaged to actively participate in group discussions and activities, picture cards are used as written in the Facilitators Guide, feedback is provided to participants during demonstrations).

**Focus Groups:** Focus group discussions will be led by the RA or study coordinator with randomly selected groups of women completing GANC throughout the study. Focus groups participants will be consented individually before they enter the focus group room so they may choose whether they want to participate. The group will be conducted in a private setting, and names will not be used during the discussion. Participants will be reminded that the discussion is private and they should avoid discussing the focus with others outside the group. Focus groups will be audiotaped to ensure accuracy of responses. Women who do not want to be audiotaped will not be included in the focus group. Audio tapes will be transcribed and will be de-identified; tapes will be destroyed immediately after transcription.

**Tracking logs:** A brief form completed by the provider each time an ANC visit is held to track the date of the session and the number of participants from the group in attendance (to track dose).

[figure not shown]
### **3.5 Intervention - Description of the Model for Group Antenatal Care**

The group ANC model was modified from a curriculum initially developed by the American College of Nurse Midwives to mobilize communities in low-resource countries for early problem identification of pregnancy related problems and referral. Using an iterative process with Ghanaian providers, pregnant women, and stakeholders as well as content experts from the U.S. to ensure local and cultural relevance and the WHO Standards for Maternal and Neonatal Care, the group ANC model was developed and tested for acceptability and feasibility by [name] and her Ghanaian team for the first time in a clinical setting in Ghana. At the core of the model is a negotiation process that acknowledges some health messaging may be in conflict with cultural beliefs. The model allows participants to incorporate safe, feasible, and culturally acceptable health beliefs into self-care actions by being inclusive of traditional practices that are not

harmful. Participants and the facilitator ‘agree’ on safe and acceptable actions within the context of the setting that are then practiced by the group.

The intervention consists of nine meetings; one individual meeting and eight group meetings. At the initial ANC visit, women are assigned to a small groups with 12-14 women of similar gestational age. Women meet individually with the midwife and the standard complete history and physical exam as well as lab tests are completed; group visits start at the second ANC visit. Prior to the start of each group, blood pressure, weight, and a urinalysis are measured for each woman. The midwife, health facility staff member, and patients then sit in circle facing one another for a 60-90 minute facilitated discussion. The health facility staff member will assist the midwife with group activities. The model uses strategies such as story-telling, peer support, and demonstration and teach-back to enhance its effectiveness. Health literacy is incorporated as an integral part of clinical practice within the model – not as an add-on to care.

Evidence-based information is presented in a non-hierarchical, patient centered, participatory way. Picture cards are used to enhance communication and learning in the group setting. They provide a mechanism to envision new concepts and ideas. The picture cards provide a valuable group discussion and learning aid to stimulate thinking and reflection, dialogue, and learning among participants. A Take Action Card booklet comprised of pictures corresponding to each topic covered in the group sessions, is provided for each pregnant woman to take home and use as a reminder of problems and actions to take if problems arise. Women are encouraged to discuss and share the information with family members and friends - reinforcing what was learned during ANC visits. Content is repeated multiple times in a variety of ways to enhance retention, including: 1) auditory (listening to stories and signs of problems); 2) visual (through use of demonstration and picture cards); 3) kinesthetically (practicing actions and “handling” picture cards); and 4) the Take Action Card Booklet for home use.

A Facilitator’s Guide for Antenatal Care developed during the Fogarty-funded study in Ghana, provides a step-by-step guide that details how to conduct each of the group ANC visits care, becoming a facilitator, enhancing adult learning, respectful maternity care, and monitoring for program quality, performance, and fidelity.

### **3.6 Control - Antenatal Care as Usual.**

The control arm is standard antenatal care delivered at health facilities in Ghana. During these visits women meet individually with a midwife who conducts a brief history and physical exam including weight and blood pressure. Following the standard ANC visit, women enrolled in the study at a control site will complete the same survey as the women in the intervention arm. Follow-up visits are the same across conditions.

### 3.7 Randomization

There are 14 sites in the study. We randomized these 14 sites into the control group and the intervention group. To improve the balance between the two groups and improve the efficiency of estimating intervention effect, we used the facility type, district of site, and ANC registrant numbers in 2018 to conduct matched randomization. The randomization process were carried out using nbpMatching package from R software.

Control Sites				Intervention Sites			
Facility	Facility Type	District	ANC 2018	Facility	Facility Type	District	ANC 2018
Adawso	Health Center	Akuapim North	403	Akuse	Hospital	Lower Manya Krobo	378
Abiriw	Clinic	Akuapim North	322	Adkukrom	Health Center	Akuapim North	299
Tetteh Quarshie	Hospital	Akuapim North	654	Atua	Hospital	Lower Manya Krobo	715
St Martin's	Hospital	Lower Manya Krobo	1081	Nsawam	Hospital	Nsawam	4930
Nsawam	Health Center	Nsawam	901	Adoagyiri	Health Center	Nsawam	817
Djankrom	Health Center	Nsawam	295	Klo Agogo	Polyclinic	Yilo Krobo	237
Nkurakan	Health Center	Yilo Krobo	469	Somanya	Polyclinic	Yilo Krobo	616

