### **3.0 Research Methods and Study Design**

To accomplish our aims we propose a cluster randomized controlled trial (cRCT) in the Eastern District of Ghana. The study is designed in collaboration with the Dodowa Health Research Center under the direction of [name] (Co-PI). Health facilities were selected based the number of deliveries and average gestational age of women in each facility and matched so that each pair of facilities are similar to each other with regard to these matching factors. For each pair of facilities, one will randomly be assigned to group ANC (intervention) and the other to routine, individual ANC (control). The locations of the chosen facilities ensure that participating facilities will be far enough apart to minimize the likelihood of cross-group contamination. The unit of randomization is the health facility stratified by site and gestational age. Cluster randomization will be produced through nbpMatching package from R software. During the study, 1680 participants will be randomized into 120 groups of 12 to 14 women of the same gestational age at the cluster site. This will result in approximately 8-10 groups per site during the study period.

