### 4.0 Data Analysis (Aims 1-3)

Data on all patients randomly assigned to the intervention or control groups will be analyzed on an intention-to-treat basis. Deviations from randomized allocation will be reported. Summary statistics based on mean, standard deviation or frequency will be used to characterize the sample distribution of each arm. Proper transformations will be investigated and taken if the sample distributions of continuous variables violate the normality assumption. For Aims 1-3, generalized linear mixed models (GLMMs) will be used to test the differences between the two arms since cluster randomized control design is used. There are four components in GLMMs: outcome variable, fixed effects, random effect, and link function. The fixed effects include explanatory variable and covariates. In this study, all three aims have the same explanatory variable which is a binary variable indicating the arm to which women are assigned. The study sites, gestational age, and women's demographic variables such as education or literacy, marital status, pregnancy history, and medical history will be added to the GLMMs as covariates to increase the precision of estimates. The random effect is the 14 facilities. In this study, a random intercept model will be used to account for the cluster effect. The outcome variables and link functions in GLMMs depends on aims and are described below. The construct of GLMMs is to test if the explanatory variable is significant at 0.05 level using likelihood ratio test.

For **Aim 1** to quantify differences in the recognition of pregnancy and newborn danger signs and knowledge of recommended action steps, the BPCR Index will be measured at enrollment and third trimester. We will add baseline data as covariates. The logit link function will be used for each binary BPCR question to test the efficacy of the group-based ANC method. The identity link function will be used when the outcome variable is a summary statistic of the BPCR Index. When the p-value of the explanatory variable is less than 0.05, we will declare a significant difference between the two arms. Average changes in BPCR summary statistics or odds ratio in each question will be used to quantify the effect of the group-based ANC intervention.

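### The analysis model names neither the matched pairs nor any matching factor, its undefined study-sites term can make the arm effect inestimable, and Sections 3.0 and 3.7 disagree on what was matched

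*Combined protocol and SAP*

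**What the plan says.** Section 3.7 (Randomization) states "There are 14 sites in the study". It gives the reason for matching, "To improve the balance between the two groups and improve the efficiency of estimating intervention effect", and the factors: "we used the facility type, district of site, and ANC registrant numbers in 2018 to conduct matched randomization". A table lists seven control and seven intervention facilities with type, district and 2018 ANC registrants. It does not say which facilities form a pair. Section 3.4 confirms the split: "We have 7 health facilities randomized to the intervention arm".

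Section 3.0 describes the design differently: "Health facilities were selected based the number of deliveries and average gestational age of women in each facility and matched". It then adds: "The unit of randomization is the health facility stratified by site and gestational age".

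Section 4.0 fits generalised linear mixed models with an arm indicator. The fixed covariates are study sites, gestational age and the women's demographic and history variables, with baseline data added for Aim 1 only. On clustering it says "a random intercept model will be used to account for the cluster effect", the 14 facilities being the random effect. Arm is tested by a likelihood ratio test at 0.05. Pair, facility type and 2018 volume do not appear, and district could enter only if that is what study sites means.

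**The concern.** There are three linked problems.

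- **The analysis does not follow the design.** The facilities were matched on three factors for balance and efficiency, and the model neither uses them nor says why not. Facility level is plausibly prognostic for facility birth, postnatal checks and morbidity (Aims 2 and 3), where no baseline value of the outcome is planned as a covariate. With seven units per arm, a chance difference in facility level stays in the arm contrast unless it is adjusted for.
- **The one facility-level fixed term is undefined.** On its literal reading it removes the comparison that the trial exists to make.
- **The design is described in two incompatible ways.** A reader cannot tell which factors to adjust for, or reconstruct the permutation distribution.

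**Working it through.** All inputs come from the Section 3.7 table and the Section 4.0 model description. The documents state no arm totals, ICC or power calculation, so the only figure to reproduce is 14 sites. The table gives 7 + 7 = 14.

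**1. The study-sites term.** Section 3.7 uses site for each of the 14 facilities and speaks of the district of a site, so site is not district there. Intercept + arm + 13 site indicators = 15 columns. Arm is constant within a facility, so the rank is 14. Adding arm gains no rank, and the likelihood ratio test of arm has zero degrees of freedom. If district was meant instead, facility type and volume remain unadjusted.

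**2. Stated factors side by side.** Section 3.0: number of deliveries and average gestational age. Section 3.7: facility type, district and 2018 registrants. No factor is common to both. The rule of stratifying by site cannot apply when the site is the unit randomised.

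**3. Realised balance (control vs intervention).**
- Type: hospitals 2 vs 3, polyclinics 0 vs 2, health centres 4 vs 2, clinics 1 vs 0. Hospitals plus polyclinics: 2 vs 5.
- District: Akuapim North 3 vs 1, Lower Manya Krobo 1 vs 2, Nsawam 2 vs 2, Yilo Krobo 1 vs 2.
- Volume: 403+322+654+1081+901+295+469 = 4,125 vs 378+299+715+4930+817+237+616 = 7,992. The ratio is 1.94 and the difference 3,867.
- Without the row holding the 4,930 site, volume is 3,044 vs 3,062. The ratio of geometric means (intervention to control) over all 14 sites is 1.23.

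**4. Could volume have been balanced?** Over all 3,432 splits of 14 facilities into 7 and 7, the smallest gap is 1,611 and the median 4,366. If the printed rows are the pairs (an assumption), every allocation gives a gap between 3,451 and 4,247. On the same assumption, a hospital-plus-polyclinic difference of 3 or more arises in 25% of allocations.

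**5. Cost of adjustment (cluster-level linear analogue).** With hospital/polyclinic vs health centre/clinic, the squared correlation of type with arm is [(5×5 − 2×2)/(7×7)]² = (21/49)² = 0.184. Variance inflation is 1/(1 − 0.184) = 1.225, and adding log volume leaves it at 1.225. Residual df fall from 14 − 2 = 12 to 10, and the t quantile rises from 2.179 to 2.228. The interval width ratio is √1.225 × 2.228/2.179 = 1.13 if residual between-facility variance is unchanged.

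**6. Pair terms instead.** Arm plus seven pair terms has full rank (8 of 8), leaving 14 − 8 = 6 df and a t quantile of 2.447. With within-pair correlation ρ of cluster means, the width ratio is √(1 − ρ) × 2.447/2.179. This falls below 1 only if ρ > 1 − (2.179/2.447)² ≈ 0.21. The documents give no ρ.

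**7. Permutation test.** Seven pairs give 2⁷ = 128 allocations, so the smallest two-sided p is 2/128 = 0.016. Dropping one pair gives 2/64 = 0.031.

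**The case against.** The strongest defence is that leaving pairs out of the model is legitimate with only seven of them. Step 6 shows that pair terms halve the degrees of freedom and help only above a correlation of about 0.21. That stands, so it cannot be said that the precision from matching is lost. What the plan lacks is a reason for the omission, or adjustment for the matching factors in place of the pairs.

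Section 4.0 makes the facilities the random effect, so its authors may not have intended 14 fixed site effects as well. That is possible, but the term is undefined and neither reading covers the three factors.

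A reader might draw stronger conclusions that the documents do not support:

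- *The randomisation failed.* The volume gap comes from one hospital, no split could have removed it, and 5 vs 2 on facility type is within ordinary chance.
- *Recruitment will be twice as large in one arm.* The volumes are 2018 ANC registrants. Section 3.0 plans roughly 8 to 10 groups at each site.
- *Facility level is clearly lopsided.* The 5 vs 2 count groups polyclinics with hospitals, and the documents do not say they belong together. Hospitals alone are 3 vs 2.
- *The result is biased by a known amount.* If facility birth differed by 10 to 20 points between facility levels (an assumption), an unadjusted contrast would shift by 3/7 of that, 4.3 to 8.6 points. With hospitals alone it would shift by 1/7, 1.4 to 2.9 points. This describes one realised allocation and a contrast without the planned covariates. It is not bias in expectation.
- *The table shows badly matched pairs.* Rows agree on type in 3 of 7 and on district in 3 of 7, but the table never says that rows are pairs.

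**Conclusion.** The point holds as a defect of specification. The model names no pair and no Section 3.7 matching factor, and gives no justification. The two descriptions of the matching conflict. The study-sites term, taken in Section 3.7's own sense, makes arm inestimable. These conclusions rest on the text and on the rank of the design, and need no outside figure.

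The realised differences in facility type and district are a reason to adjust, but they are not evidence of faulty randomisation. How far adjustment would move or sharpen the estimates cannot be determined, because the documents give neither between-facility variance nor the prognostic strength of the factors. The plan should be corrected before analysis.

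**What to change.** 1. **Model.** In every GLMM, delete study sites as a fixed effect and keep the facility random intercept. Add facility type and log 2018 ANC registrants. Fix the grouping of facility type in advance: polyclinics occur only in the intervention arm and the clinic only in the control arm, so a four-level factor would take those sites out of the comparison.
2. **District.** Say explicitly that district is left to a sensitivity analysis because four districts cost 3 further df.
3. **Pairs.** List the pairs produced by nbpMatching. Report a within-pair permutation test as a sensitivity analysis only, stating its smallest attainable p of 0.016. In a Holm family of three outcomes (an assumption about family size) the first threshold is 0.05/3 = 0.0167, so the test can only just reach it, and with one pair dropped it cannot.
4. **Section 3.0.** Replace the matching factors and the stratification sentence with what was actually done.

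The cost is plan wording, since the facility data are already in the Section 3.7 table. The statistical price is 2 between-facility df plus the collinearity of facility type with arm. Under the hospital/polyclinic grouping, intervals would be up to about 13% wider if the factors explain no between-facility variance, and narrower than that to the extent that they do.
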